Will change in lifestyle have a correlation with ability to work? Life style factors that affect work participation

Occupational rehabilitation for people with body mass index
above 30

Summary

This trial will follow up a group of people with BMI above 30 and who have participated in an occupational rehabilitation program at Muritunet. The aim of this study is to gather information about how life style changes affect the ability to work.

Ver.2.0, 24.7.2017

[name]
[contact]

1 Introduction

Numbers from Statisk Norway indicate that one out of three has overweight (BMI >25) or obesity (BMI >30) in the population in the age of 16 to 74 [1]. Development of overweight and obesity have the latest years dramatically increased. In Norway, the consequences of this development is an epidemic situation with an increase in life style diseases and work absence. Central Norway Regional Health Authority (HMN RHF) has initiated action to reduce work absence and consequence of obesity by introducing a work related rehabilitation program for people with BMI above 30. Combination of weight loss programs and work related intervention is new in Norway. Outcomes of this intervention are so far are not known.

The trial can be used to improve the quality of occupational rehabilitation in Norway in the Specialised Health Care services. Others who work with life style changes and with work related rehabilitation can also use the collected information. This study is a Cohort clinical trial with a Pseudo prospective design.

1.1 Status of knowledge

Development of overweight and obesity is one of the three biggest health challenges in Norway. Overweight and obesity influence the person's life quality, psychiatric and physical health and social life [2]. Overweight and obesity associates with high comorbidity and illnesses such as muscular and skeletal problems, lung diseases, cancer, social isolation, stress, psychiatric diagnoses and early death [3-6]. Higher BMI gives more complications [7]. The reason for obesity is complicated since many factors affect. Individual factors as the personal life style, society, culture, socio-economic status, genetic and biological factors influence the development [8].

High BMI and the consequence of obesity gives challenges for the individual, for the society and the occupational. Studies in the latest years indicate that high BMI is increasing longer periods with work absence [9] and that there is directly context between high BMI and long-term sick leave above seven days [3, 10]. Obesity contributes to independent factor to work absence and indirect thru lifestyle related illnesses.

Long-term sick leave also affects the society with cost cause reduced work productivity and increasing Social Security benefits [10]. A study from Denmark refers to that obesity contribute to yearly 1,8 million extra days of work absence and closely to 1.100 cases of disability pension related to obesity [11]. In a study on Swedish women concludes that overweight and obesity cause ten present of the total cost regarding social security. A rapport from OECD through Statisk Norway shows that persons in the age between 50 to 59 with obesity have three times as much work absence than those that don't have obesity [12]. The reasons for work absence is complexed. Factors that contribute is disease and symptom from the muscular and skeletal system, mental disorders, relation at the workplace, family relationship and socioeconomic issues.

A person with a long-term sick leave in Norway can participate in an institutional work related rehabilitation stay. The aim for such stay is to increase function and work ability to prevent the individuals permanent to fall out of working life [13]. The intervention in occupational rehabilitation builds on physical activity, cognitive therapy, and cooperation with Norwegian Labour and Welfare Administration (NAV), employer and others that can contribute to deal with the health challenge and to increase work ability. The intervention based on the World Health Organisation's classification of health and health-related domains, known as The International Classification of Functioning, Disability, and Health, ICF. ICF is the WHO framework for measuring health and disability at both individual and population levels, known as a bio-physio-social framework [14-16]. Many studies

indicate that occupational rehabilitation can be an effective intervention to reduce sick leave and disability benefit [13].

People with high BMI needs beside work rehabilitation also focus on life style changes to reduce consequences of obesity. The basic treatment of obesity is a focus on cognitive treatment that helps people changing diet and increasing activity.

In Norway, there is entirely 340.000 humans with overweight and obesity in the age between of 20 to 76. Obesity cost yearly for the western countries 2 to 7 present of the national health budget [17]. In Norway, people with obesity can participate in weight loss programs in specialized institutions that focus on life style treatment.

1.2 Knowledge challenge

Occupational rehabilitation with a focus on weight loss program is new in Norway, and just a few institutions offer this kind of intervention. The consequence of this extent is little knowledge, experience, and few studies were done in the crossing fields between occupational rehabilitation and rehabilitation generally [18] and in work related rehabilitation individually [19].

Life style changes take time. The weight loss program needs to focus on changes in diets, physical activity, and cognitive therapy [20]. The primary challenge with weight loss programs is that the body weight gain with a third of the total weight loss within a year. Studies show that about fifty present of those who participate in weight loss programs going back to their original weight after five years [21]. There is a lack of documentation on what kind of life style treatment that gives a good effect, both in and outstay [22]. Therefor life style treatment is often given without proper documentation for what intervention that works or not [23].

Today many unknown factors affect in between obesity and sick leave. The challenge is that traditional occupational rehabilitation does not include weight loss programs, and weight loss programs don't include the focus on work participation. There is also in the field of work related rehabilitation lack of knowledge about effect full interventions that can reduce sick leave and disability pension in people with nonspecific muscular and skeletal problems, obesity and psychiatric disorder [24]. Besides lack of information on the effect of occupational rehabilitation, few studies have focused on the mechanism that can be effect full between obesity and sick leave [10], on individual factors that generate changes in life style [8, 25] and what will make work participation [26].

1.3 Background

In 2015 established HMN RHF an occupational rehabilitation program for people with BMI above 30 who might be or is on sick leave directly or indirect cause obesity. This program combines work participation and life style changes and exists only in two institutions in Norway. The goal of the program is to increase function and work ability and weight loss. The program is new, and few documents exist on the effect and the correlation between life style changes and work ability. There is also need to question whether obesity is the reason for work absence or is there other factors that affect work ability. This study wants to follow up a group of people who have been participating occupational rehabilitation at Muritunet.

1.4 Research fields meaning for patient treatment and disciplines

This trial can contribute to improving the quality of work related rehabilitation in the specialized health care services and for other institutions who work with obesity and occupational rehabilitation. The study can also contribute to:

1. Participants in this trial might get the opportunity to increase their knowledge about their health and function that affect their everyday living.
2. New research-based knowledge and professional development in the crossing field between obesity and work participation.
3. New insights about effective interventions that can contribute to reducing the number of sick leave and long lasting weight loss.
4. Documentation of result over time for the group that has participated in the professional program for people with BMI above 30.
5. Developing the program for people with BMI above 30.
6. Increasing political focus on a fast growing group.
7. Indirect social-economic and individual benefits.

2 The research question and goal

Lifestyle is a field that contains several areas. It tells us about how persons live their life measured in physical activity, diets, inactivity, intoxication, smoking, alcohol, circadian rhythm, sleep behavior and stress. The focus for people in life style changes is weight loss through reducing energy consumption and increasing energy consumption through physical activity [27] with the help of cognitive methods. One of the goals is to reduce the weight with 5 to 10 percent. This reduction will accumulate health benefits as better life quality, reducing life style diseases and better mental and physical health and this health benefits will gain the society. Several studies indicate that there is an association between high BMI and sick leave [3, 10, 28]. The question is what correlation is there between life style changing and work participation. What motivates people to work and what happens with the sick leave when BMI is decreasing?

The purpose of this trial is to get more information about how life style changes affect work participation for people with BMI above 30. The information can contribute to improving the quality of occupational rehabilitation programs in the specialized health care services and for others who work with weight loss programs and work related rehabilitation programs.

The primary goal of this trial: What correlation is there between life style changing and work participation after participating in occupational rehabilitation on Muritunet?

Aims of the trial are:

1. Will changes in physical activity, diets, and life quality correlate with work participation?
2. Will changes in physical activity, diets, and return to work self-efficacy correlate with life quality?
3. Will changes in work participation, life quality, and diets correlate with weight changes?
4. What experience the participants as important factors to achieve lifestyle changes and work participation?

Work participation defined in this study is working full time or partial with an employer, permanent or temporary or as a student. The employee has to work coherently in 28 days without to receive social benefits.

Life quality defines in either in a subjective or an objective perspective [29]. In this study, the subjective perspective emphasizes the individual's positive, negative, cognitive and emotional experience that concern life quality.

Diet in this study is the intake of food and liquid that shall ensure a satisfying amount of calories, nutrient and prevent life style diseases.

Physical activity in this study is action made by musculature in a way that it results in increased energy consumption higher than resting.

3 Implementation

3.1 Design, methods and analyze

This study will follow-up a group of people with BMI above 30 over a period of one to four years. Study with a Pseudo prospective design that includes collecting data through both qualitative and quantitative methods. Both methods will take place at the same time, Parallel mixed Methods. The data is linked to each other in the different stages in the study, and the methods will confirm, cross-validate or confirm findings in one method with another result in another process. Creswell uses the Current concept Triangulation [30]. The purpose of this plan is to make one method stronger with using the strength of another method.

The definition of Mixed Method research in this study is; Approach to gathering data through quantitative and qualitative methods with the use of designs that involve both philosophical and ethical theory [31].

Collecting data through forms, physical test, journal, interviewing, from national register from the Norwegian Labour and Welfare Administration and National

Education Data Base. Using registry data will be useful because there might be a link between different variables that might contribute to clarify the association between health and work participation. It then can be specified whether the participant is on sick leave because of obesity related issues or if there are other reasons for the sick leave. Another example is the connection between education and work participation because the level of education may have importance for choice of profession and sick leave. There are several links in this study that can strengthen the findings in the data collection.

Data collected at four different stages.

1. Baseline (BL). From the beginning of the stay at Muritunet. Data gathered from the journal, from self-reported forms, and from a physical test. The particular data package is; in and out date for the stay, age, sex, diagnosis, education level, health problems, work status, social benefits, changing in work status, work place, expected work time pr. Week and occupation code, work motivation, income, diet, physical capacity and activity, life quality and overeating behaviour.
2. T1, six months after the first stay at Muritunet. Data gathered from the journal, from self-reported forms, and from a physical test. The particular data package is; in and out date for the stay, diagnosis, health problems, work status, social benefits, changing in work status, work place, expected work time pr. Week and occupation code, work motivation, income, diet, physical capacity and activity, life quality and overeating behaviour.
3. T2, 12 months after the first stay at Muritunet. Data gathered from the journal, from self-reported forms, and from a physical test. The particular data package is; in and out date for the stay, diagnosis, health problems, work status, social benefits, changing in work status, work place, expected work time pr. Week and occupation code, work motivation, income, diet, physical capacity and activity, life quality and overeating behaviour.
4. T3, Focus group interview, one to four years after the participants finishing their stay at Muritunet.

5. T4, Data collecting from Norwegian patient register (NPR) and National Education database (NUDB). Will be collected once. Data collected are social benefits as sick leave, work assessment allowance, disability benefits, unemployment benefits, diagnosis for sick leave, changing in work employment, work place and expected work time pr. A week and occupation code.

Some participants will return to their work, but some will not. It will lead to variation for my chose of how to design methods and analyze the data material. Different ways will complete each other, and today it is common to use several methods and models in the same study.

Data analysis is chosen on the background of design and approaches. BL, T1, and T2 is a typical quantitative approach and will be analyzed both on its own, but also compared with data collected in T3 and T4. The qualitative interview will have open-ended questions, and the participants will get the opportunity to reflect on themes defined from the data collection earlier in the study.

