3.7 Register data

NAV and NUDB have reliable information about work participation and education data. The data will contain information about social benefits as sick leave, work assessment allowance, if the participant is registered as a job seeker, changing in work employment, income, about the work place and expected work time pr. Week, occupation code and about education. Collecting data at the end of the study and correlating with data from the foams, journal and qualitative interview.

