3.9 Analyse

The goal of this study is to explore the correlation between life style changing and work participation. Four secondary issues will result in using different ways of analyzing the data material. In this way, each issue can be investigated on their own, but also analyzed with each other.

The primary analyzing approach for this study is multivariate logistics regression analysis with a focus on the correlation between several independent variables (X) and dependent variables (Y). In the main issue Y= work, and X= physical activity (x1), diets (x2) and life quality (x3). Work divides into three categories; a) full time working, b) part time working, c) not working. In the secondary issue, is Y= life quality and X= physical activity (x1), diets (x2), and the belief in managing (x3).

In the quality research, thematic methods will be used to analyze the interviews. This method can catch the significant complexity in the text and is the most usual way to analyze a text in qualitative research. This way of analyzing consist of six steps. 1. Transcribing data, 2. Reading and re-reading the data, 3. Coding, 4. Search after subjects, 5. Define and give a name to the subjects, and 6. Choose to illustrate examples of different issues.

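### The written work model omits education, which the protocol says may matter for sick leave and collects at baseline; the lifestyle–work association is open to confounding of unknown size

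*Protocol*

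**What the plan says.** Section 3.9 names the method ("The primary analyzing approach for this study is multivariate logistics regression analysis") and then lists the terms: "In the main issue Y= work, and X= physical activity (x1), diets (x2) and life quality (x3"). The outcome has three levels: "Work divides into three categories; a) full time working, b) part time working, c) not working". No further covariate is named, and no section of the protocol mentions adjustment or stratification.

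Section 3.1 gives education as an example of a link that register data can clarify: "the level of education may have importance for choice of profession and sick leave". The baseline package in the same section contains "in and out date for the stay, age, sex, diagnosis, education level, health problems, work status, social benefits". Section 3.7 adds a second source, stating that "NAV and NUDB have reliable information about work participation and education data", and says that register data will be correlated with the forms, the journal and the interviews.

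Section 2 words the aim in two ways. The primary goal and the numbered aims ask about correlation. The purpose statement asks "how life style changes affect work participation for people with BMI above 30".

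**The concern.** The protocol identifies education as relevant to the outcome side of its main question, arranges to collect it, and then writes a main model without it. There is no comparison group, so the regression coefficient carries the whole argument. If participants with more education both change their lifestyle more and find it easier to return to work, the three-predictor model would show a lifestyle–work association even if lifestyle change did nothing for work. Section 2 wants the answer for improving rehabilitation programmes, and that use depends on the association not being a by-product of who had more education.

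**Working it through.** **Text check.** Education: linked to profession and sick leave (3.1), collected at baseline (3.1), available again from a register (3.7), absent from the work model (3.9). Section 1.1 lists socioeconomic issues among the causes of work absence and socio-economic status among the influences on obesity. No section links education to *change* in activity, diet or life quality. The outcome side of the confounding path is thus in the document and the exposure side is an assumption. The protocol gives no figure to reproduce on this point.

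**Direction, by exact calculation.** Assumptions: activity has no effect on work, 40% have higher education, and 40% of the less educated work (odds 0.4/0.6 = 0.667). Let *w*₁ and *w*₀ be the proportions working with higher and lower education. Among the active, the share with higher education is *e*₁ = 0.4·*a*₁/(0.4·*a*₁ + 0.6·*a*₀), where *a*₁ and *a*₀ are the proportions active by education. *e*₀ is the same share among the inactive. The proportion working in each group is *e*·*w*₁ + (1−*e*)·*w*₀.

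- Weak case: education odds ratio 2, so *w*₁ = 1.333/2.333 = 0.571. Active 50% against 40%: *e*₁ = 0.20/0.44 = 0.455 and *e*₀ = 0.20/0.56 = 0.357. Working 0.478 against 0.461, giving an unadjusted odds ratio of 1.07.
- Strong case: education odds ratio 4, so *w*₁ = 2.667/3.667 = 0.727. Active 70% against 30%: *e*₁ = 0.28/0.46 = 0.609 and *e*₀ = 0.12/0.54 = 0.222. Working 0.599 against 0.473, giving an unadjusted odds ratio of 1.67.

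The true value is 1.00 in both.

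**Size at the planned sample, by simulation.** Section 3.10 gives 51 participants for the work target and 59 for the weight target, the largest of its three; both were used. Assumptions: binary work outcome with logit(work) = logit(0.4) + ln(OR)·education, 40% with higher education, three standardised predictors with no true effect, lifestyle change higher by 0.2–0.8 SD with more education, education odds ratio 1.5–4, and a two-sided 5% test.

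- Over the whole grid, the unadjusted bias in the log odds ratio per SD is about 0.02–0.26, that is an odds ratio of e^0.02 = 1.02 to e^0.26 = 1.30 where the truth is 1. False positives are about 4–13% unadjusted and 4–6% adjusted.
- Odds ratio 1.5, 0.5 SD (n = 59): bias 0.06; false positives 4.6% unadjusted, 4.0% adjusted.
- Odds ratio 2, 0.5 SD (n = 59): bias 0.09; 6.5% against 5.8%. Simulation error is about 0.7 points, so these do not differ clearly.
- Clear inflation, from about 9% upwards, appears only at odds ratio 4 with 0.5–0.8 SD.

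**Cost of the extra term.** The standard error rises by about 2–13% with a binary outcome; at n = 51 with 0.5–0.8 SD the top of the range can reach about 15%. At odds ratio 2 and 0.5 SD, root mean squared error goes from 0.316 to 0.331 after adjustment, a rise of 0.331/0.316 − 1 = 5%. With a multinomial fit of the three categories each covariate takes two slopes: from 6 to 8 slopes, or from 51/6 = 8.5 to 51/8 = 6.4 participants per slope. With an ordinal or binary fit the slopes go from 3 to 4.

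**The case against.** The strongest reply is that section 3.9 is an outline. It does not call the model complete or unadjusted, covariate lists are commonly left to an analysis plan, and sections 3.1 and 3.7 show that education is meant to be used somehow. A reader might infer that the protocol excludes adjustment or contradicts itself. Neither inference is supported: it is silent on adjustment. What remains is that it does not leave the model open. It spells out the X terms, and the only use stated for register data is correlation with the other sources.

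Second, the primary goal is a correlation, and for a purely descriptive correlation the three-predictor coefficient is not biased. That stands. The concern applies to the purpose statement in section 2 and to any use of the result to shape programmes.

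Third, a reader might infer that leaving out education does bias the lifestyle coefficient. The documents do not support that. Everyone enrolled has a BMI above 30, so a link between socio-economic status and becoming obese does not tell who changes more during the programme.

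Fourth, the sample is small and adjustment can cost more than it gains. This also stands for the weaker settings, and it argues for reporting both models rather than replacing one. Education is also only one of several collected baseline variables outside the model. It is singled out because the protocol itself names it.

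**Conclusion.** The point holds as a weakness in how the main model is specified, not as a demonstrated bias. The protocol flags education, collects it, and writes a work model that cannot separate it from lifestyle change. The likely effect ranges from negligible (log odds ratio bias near 0.02, false-positive rate unchanged) to material (bias near 0.26, false positives about 13%). The material end needs both a strong education–work link, with an odds ratio around 4, and at least a half-SD difference in lifestyle change. These inputs are assumptions, as are the binary outcome and the 40% proportions. The change is worth making because the data are already planned, but the stated correlation goal is not invalidated without it.

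**What to change.** In section 3.9, add baseline education in two levels to the work model, with the cut point and the source (baseline form or register) fixed before analysis. Report this adjusted model beside the stated three-predictor model, so that a reader sees how far the coefficients move. Limit parameters by using an ordinal or binary work outcome, or a penalised (Firth) fit if cells are sparse. Word the result as an association in both models.

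The cost is wording only, since no new data are needed. The statistical price is confidence intervals about 2–13% wider with a binary outcome, more with a multinomial one, and a slightly larger total error if confounding by education turns out to be weak.
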